6.2.1.1 Packaging and labelling

Xonrid® will be manufactured and provided for the study by Helsinn Healthcare SA, the Sponsor of this clinical investigation.

The study product shipment to the study site will be done only after the completion of all Ethics and Administrative procedures.

The product will be labeled as experimental treatment in accordance with Good Manufacturing Practice (GMP, Annex 13).

The primary package is a bottle containing 75 ml of gel. Subjects randomized to Xonrid® + SOC will receive a total of:

1. no. 12 bottles if head & neck cancer subjects
2. no. 4 bottles if breast cancer subjects.

The number of bottles assigned should be enough for the whole study duration (56 ± 2 days / 63 ± 2 days).

6.2.1.2 Study device instructions for use

Patients will be instructed to apply Xonrid® on the irradiated area three times daily, the first application 1–2 h after the morning radiotherapy (RT) session, the second in the early afternoon, and the third in the evening, starting on the first day of irradiation.

Head & neck cancer subjects will use 12-18 puffs for each application.

Breast cancer subjects will use 6 puffs for each application.

The skin will be perfectly clear before the irradiation.

The treatment with Xonrid® will continue until 2 weeks after the completion of the radiation treatments or until the development of Grade ≥ 3 skin toxicity.

When G3 toxicity occurs, the subject has to discontinue the study and the skin toxicity will be managed according to site internal guidelines. The use of other topical medications for the treatment of dermatitis, in particular topical steroid creams, is not allowed.

When the subject does not receive RT, e.g. during the weekends, Xonrid® has to be applied every day in the morning, afternoon and evening.

The treatment duration for each subject will be of maximum 58-65 days respectively for breast and head & neck cancer, or until G3 skin toxicity.

6.2.1.3 Handling and storage

It is the Investigator/Institution's responsibility to set up a system for handling the clinical investigation treatment, so as to ensure that:

- deliveries of product supply from the Sponsor are correctly received
- products are handled and stored safely and properly in a secured area
- treatments are only dispensed to study subjects in accordance with the clinical investigation plan
- any unused, used, partially used product is returned to the Investigator (including empty bottles).

The study product shall be carefully stored at the study site, in a safe area and separately from other drugs/products. It shall be stored in a dry and cool place, away from direct sunlight or heat.

The pharmacist and or the Investigator shall maintain records of the study products receipt by the study site and an updated inventory of the study product.

Treatments will be dispensed to the subjects enrolled in this clinical investigation only by authorized personnel.

After study conclusion, all unused study product shall be returned to the Sponsor or destroyed after written Sponsor approval.

6.2.1.4 Study product accountability and compliance

The Investigator is responsible for ensuring the accountability of the study product.

Accountability records will include:

- confirmation of product delivery and receipt to/at the clinical site
- records concerning the product delivery to each subject and the return from each subject
- the return to the Sponsor or alternative disposition of unused products.

The Investigator should maintain records that adequately document:

- that the subjects were provided with the doses specified by the clinical investigation plan/amendment(s)
- that all products provided by the Sponsor were fully reconciled.

Unused products must not be discarded or used for any purpose other than the present clinical investigation.

Products that has been allocated to one subject must not be re-dispensed to a different subject.

Subjects will be reminded of the importance of strictly complying with the instructions received from the Investigator and to return all unused treatment or empty bottles to the Investigator.

The Monitor, at monitoring visits, will verify the products accountability and will check all products returned by the subjects (unused, used and partially used) before arranging for their return to the Sponsor.

Compliance to the treatment will be checked by the Investigators when the subjects are bringing back to the Site the used/unused products. A cross check will be done with patient's diary information.

The treatment compliance will be then evaluated by weighing the bottles before return to the Sponsor.

6.2.2 Standard of Care (SOC)

The SOC preemptive treatment will be according to MASCC guidelines and it includes:

1. washing with lukewarm water and a mild pH-neutral or non-alkaline soap. Shaving with a sharp, disinfected wet razor or with non-traumatizing electric razor
2. during or after radiation treatment, avoiding the use of metallic-based topical products (zinc oxide, creams or deodorants with an aluminum base, for instance), because they may increase the surface dose to skin
3. wearing loose-fitting clothes in order to prevent friction injuries over the irradiated area
4. avoiding extreme temperatures
5. avoiding the use of tapes and adhesives.

All the subjects enrolled in this clinical investigation will be recommended to comply with SOC guidelines above listed. SOC will be followed every day, continuatively, since the beginning of the radiotherapy until 2 weeks after the last RT session.

In the treatment group with SOC alone, when G2 skin toxicity develops, an adjunctive standard treatment will be introduced, at discretion of the Investigator.

Should G3 skin toxicity develop, then, in any case, the study will be interrupted and the subject will be treated according to the Investigator's opinion.

6.2.3 Concomitant medications

Any medications (other than those excluded by the clinical investigation plan) that were considered necessary for the patients' well-being and do not interfere with the study product can be given at the Investigator's discretion.

According to exclusion criteria, the following prior and concomitant medications are prohibited:

- concurrent cetuximab;
- previous radiation therapy on the head and neck area or breast and thorax areas;
- use of a tissue-equivalent bolus;
- over-the-counter topical medications containing steroids.

In the treatment group with SOC alone, when G2 skin toxicity develops, an adjunctive standard treatment will be introduced, at discretion of the Investigator. The treatment will be recorded in the appropriate section of the CRF.

6.3 Subjects

In this clinical investigation 80 subjects will be enrolled: 40 of them will be female affected by breast cancer and 40 will be male and female affected by head & neck cancer, undergoing to postoperative or curative radiation treatment. All the subjects will be randomized to Xonrid® + SOC or SOC alone, only if they fulfill the following eligibility criteria:

6.3.1 Inclusion criteria

1. Male and female which are 18 years of age or older
2. Performance status < 2
3. Epithelial carcinoma of oropharynx, nasopharynx, larynx, hypopharynx, paranasal sinus and salivary glands or breast cancer, planned to receive a total dose of at least 50 Gy
4. Postoperative or curative radiation treatment
5. Concurrent chemotherapy is accepted, in head & neck cancer patients
6. Patients willing and able to give signed informed consent and, in the opinion of the Investigator, to comply with the Clinical Investigation Plan tests and procedures.

6.3.2 Exclusion criteria

1. Pregnant or lactating women
2. Planned to receive concurrent cetuximab
3. Previous radiation therapy on the head and neck area or breast and thorax areas
4. Cutaneous and connective diseases (i.e. lupus erythematosus or scleroderma)
5. Systemic diseases known to delay the skin healing process such as diabetes mellitus or severe renal failure

6. Use of a tissue-equivalent bolus
7. Use of over-the-counter topical medications containing steroids
8. Presence of rashes or unhealed wounds in the radiation field
9. Recent sun exposure
10. Mental conditions that could adversely affect patients' adherence to the study.

Should G3 skin toxicity develop, then, in any case, the study will be interrupted and the subject will be treated according to the Investigator's opinion.

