Phase of the study	Screening	RT & treatment start	RT (expected 33-35 sessions)							RT end	2 weeks treatment without RT
Visit number	1	2	3	4	5	6	7	8	9	10	
Week	-	0	1	2	3	4	5	6	7	9	
Time (Days) ± 2 days	-3 to 0	1	7	14	21	28	35	42	49	63	
Informed consent signature	X										
Inclusion/Exclusion criteria	X	X									
Patient randomization		X									
Socio-demographic data	X										
Medical and surgical history collection	X										
Physical examination	X	X	X	X	X	X	X	X	X	X	
Concomitant medications and therapies	X	X	X	X	X	X	X	X	X	X	
ECOG performance status	X										
Erythema assessment	X	X	X	X	X	X	X	X	X	X	
Skindex-16 questionnaire	X	X	X	X	X	X	X	X	X	X	
Spettrophotometry & TEWL		X	X	X	X	X	X	X	X	X	
Study treatment dispensation to patient		X								X	
Study treatment return and accountability										X	X
Patient diary dispensation		X								X	
Patient diary collection										X	X
Patient Global Satisfaction score										X	X
Adverse events		X	X	X	X	X	X	X	X	X	

Table 2: Study Flow-Chart for breast cancer subjects

Phase of the study	Screening	RT & treatment start	RT (expected 30 sessions)						RT end	2 weeks treatment without RT
Visit number	1	2	3	4	5	6	7	8	9	
Week	-	0	1	2	3	4	5	6	7	8
Time (Days) ± 2 days	-3 to 0	1	7	14	21	28	35	42	56	
Informed consent signature	X									
Inclusion/Exclusion criteria	X	X								
Patient randomization		X								
Socio-demographic data	X									
Medical and surgical history collection	X									
Physical examination	X	X	X	X	X	X	X	X	X	
Concomitant medications and therapies	X	X	X	X	X	X	X	X	X	
ECOG performance status	X									
Erythema assessment	X	X	X	X	X	X	X	X	X	
Skindex-16 questionnaire	X	X	X	X	X	X	X	X	X	
Spettrophotometry & TEWL		X	X	X	X	X	X	X	X	
Study treatment dispensation to patient		X							X	
Study treatment return and accountability									X	X
Patient diary dispensation		X							X	
Patient diary collection									X	X
Patient Global Satisfaction score									X	X
Adverse events		X	X	X	X	X	X	X	X	

Table 3: CTCAE v4.0 Term Dermatitis Radiation

Grade 1	Grade 2	Grade 3	Grade 4	Grade 5
Faint erythema or dry desquamation	Moderate to brisk erythema; patchy moist desquamation, mostly confined to skin folds and creases; moderate edema	Moist desquamation in areas other than skin folds and creases; bleeding induced by minor trauma or abrasion	Life-threatening consequences; skin necrosis or ulceration of full thickness dermis; spontaneous bleeding from involved site; skin graft indicated	Death

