Subjects will receive their planned radiotherapy treatment and will be constantly followed by clinicians. The study visits will be done every week. Participants will undergo a careful, frequent and accurate evaluation of their irradiated area equal if not better than what is the normal practice for subjects undergoing radiotherapy.

In the case a subject allocated to the group “SOC alone” develops a G2 skin toxicity, an additional treatment will be introduced, according to the Investigator’s opinion.

Should a G3 skin toxicity develops the subject will immediately interrupt the study treatment and the study participation. The Investigators will thereafter choose the best treatment for that subject.

In the light of the above, no additional risk arising from the participation to this clinical investigation can be envisioned.

5. Objectives and hypotheses of the clinical investigation

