6.2 Investigational device and comparator

6.2.1 Xonrid®

The product under investigation is Xonrid®.

Name: Xonrid®

Formulation: Gel

Route of administration: Topical

Composition: the composition of Xonrid®, including ingredient function, as reported in the commercial available product, is reported in Table 4.

Xonrid® is a short term use, Class IIa Medical Device, a topical gel designed for RT-induced dermatitis. When applied to the target skin areas, Xonrid® forms a protective film, reduces the trans-epidermal water loss (TEWL) effect induced by external factors and increases moisturizing. The component responsible for the formation of this film is mainly Hyaluronic Acid, that also helps to achieve an optimal moisturizing effect. The other components responsible for the formation of this film are: polyacrylamide gluconolactone, and Xanthan gum. In particular, gluconolactone is a polyhydroxy acid, with a strong hygroscopic moisturizing power, as well as a glycerin effect. Moreover, the device includes sweet almond oil, known for its emollient, softening, nourishing and soothing properties, and is particularly effective in the treatment of dry, reddened and sensitive skin areas. It promotes the healing process by restoring the physiological hydration levels of the affected skin areas. It can be applied to the target areas including skin folds and creases, either presenting or not minor traumas or abrasions. On these bases, Xonrid® may represent a promising device for the prevention of radiation dermatitis.

Table 4: Xonrid® ingredients with relative function

Ingredient	Function
Glycerin (Glycerol)	Humectant
Gluconolactone, sodium benzoate, calcium gluconate	Preservative
Chamomilla recutita water	Masking agent
Xanthan gum	Rheology additive
C12-15 alkyl benzoate	Emollient
Ethylhexyl palmitate	Emollient
Disodium EDTA	Chelanting agent
Glyceryl stearate	Emollient
Prunus amygdalus dulcis oil	Emollient
Polyacrylamide, C13-14 isoparaffin, laureth-7	Viscosity increasing agent
Vitis vinifera extract, aqua, propylene glycol	Skin conditioning agent
Aqua	Solvent
Sodium hyaluronate	Skin conditioning agent
Propylene glycol, aqua, camelia sinensis extract	Skin conditioning agents
Propylene glycol, hydrolyzed RNA, hydrolyzed DNA	Skin conditioning agents

Raspberry ketone	Skin conditioning agent
Propylene glycol	Solvent
Tocopheryl acetate	Preservative/ Antioxidant agent

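### The eligibility criteria do not exclude patients with a known allergy to a gel ingredient: mainly an avoidable safety gap, with a possible but unquantified effect on grading in Group A

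*Protocol*

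**What the plan says.** Protocol 6.3 makes the criteria the condition for entry: "All the subjects will be randomized to Xonrid® + SOC or SOC alone, only if they fulfill the following eligibility criteria". Of the ten exclusions in 6.3.2 (repeated in the synopsis), two come closest to skin sensitivity. Item 4 is "Cutaneous and connective diseases (i.e. lupus erythematosus or scleroderma"), and item 8 is "Presence of rashes or unhealed wounds in the radiation field". No item mentions allergy, hypersensitivity or contact sensitivity. Inclusion 6 and exclusion 10 concern consent, ability to comply and adherence. The prohibited treatments in 6.2.3 and the instructions for use in 6.2.1.2 are silent as well. SAP section 10 restates the exclusions and adds nothing on this.

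The gel has many ingredients. Table 4 in 6.2.1 includes "Prunus amygdalus dulcis oil", chamomile water, propylene glycol and several plant extracts, and the text says that "the device includes sweet almond oil, known for its emollient, softening, nourishing and soothing properties". Exposure is repeated: "Patients will be instructed to apply Xonrid® on the irradiated area three times daily". Section 4 ends its risk assessment by saying that "no additional risk arising from the participation to this clinical investigation can be envisioned".

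For the endpoint, Table 3 defines grade 2 by signs alone: "Moderate to brisk erythema; patchy moist desquamation, mostly confined to skin folds and creases; moderate edema". Protocol 6.4.2 and SAP 9.1 describe assessor training and a third reader when the first two disagree. Neither says how to separate a contact reaction from a radiation effect.

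**The concern.** A known allergy to an ingredient is foreseeable, can be asked about before randomisation, and bears directly on a product applied to skin that is also being irradiated. The written criteria let such a patient in, and the risk section does not consider the possibility. The safeguard in Protocol 16.1, discontinuation for an unsafe adverse event, acts only after exposure.

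There is a second, smaller issue of measurement. Only Group A is assigned the gel. Group B's adjunctive treatment starts only once G2 has developed, when the patient has already had the event of interest. A reaction to the gel can therefore touch the primary endpoint in one arm only. If it shows as erythema in the field and is read as radiation dermatitis, it counts as a failure for the gel. Protocol 14.3 keeps signs regarded as lack of efficacy out of the adverse event section unless the investigator sees another cause or the event is serious. A misread reaction could then also be missing from tolerability, which SAP 12.3 bases on application-site events.

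**Working it through.** **Step 1: does any written provision cover the case?** Take a patient with a documented allergy to a Table 4 ingredient and intact skin at entry.

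- Exclusion 4: as worded, the bracket limits the item to lupus erythematosus or scleroderma. Not met.
- Exclusion 8: needs a rash or wound already present in the field. Not met.
- Inclusion 6 and exclusion 10: about consent, compliance and adherence. They do not bar the patient.
- Visit 1 medical history (6.4.1): would probably reveal the allergy, but no criterion acts on it.

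The patient is eligible as written.

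**Step 2: the plan's own figure.** Inputs from Protocol 7.1: p1 = 0.382, p2 = 0.829, two-sided alpha 0.05, power 80%. The mean proportion is 0.6055.

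n = [1.960·√(2·0.6055·0.3945) + 0.842·√(0.382·0.618 + 0.829·0.171)]² / (0.447)² = (1.355 + 0.517)² / 0.1998 = 17.5, so 18 per group. With 10% dropout, 18/0.9 = 20. The plan's figures reproduce (power 81.1% at 18 and 85.3% at 20), and this point disputes none of them.

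**Step 3: how likely is it that such a patient is present?** The documents give no prevalence, so r is an assumption. SAP 9.1 analyses each cancer site separately, which means 20 planned gel users per site. P(at least one) = 1 − (1 − r)^20:

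- r = 1%: 1 − 0.99^20 = 18%
- r = 2%: 1 − 0.98^20 = 33%
- r = 5%: 1 − 0.95^20 = 64%

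Over both sites (40 gel users) the same formula gives 33%, 55% and 87%. All of these are chances that an allergic patient is enrolled in the gel arm. A misgraded failure also needs a reaction, a grade of G2 or higher that counts at week 5, and a patient who would otherwise have been G2-free.

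**Step 4: what could misgrading do to power?** Let q be the share of otherwise G2-free gel patients whose contact reaction is graded G2 or higher. The Group A rate becomes 0.829·(1 − q). At 20 per arm:

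| q (assumed) | Group A rate | Power |
|---|---|---|
| 0 | 82.9% | 85.3% |
| 1% | 82.1% | 83.6% |
| 2% | 81.2% | 81.8% |
| 5% | 78.8% | 76.0% |
| 10% | 74.6% | 65.1% |

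Exact enumeration of the Pearson test gives 85.4%, 75.5% and 64.1% at q = 0, 5% and 10%, so the approximation is adequate. If allergy is unrelated to radiation response, q from known allergy cannot exceed r. For an assumed prevalence of 1% to 2%, the power loss is then at most 1.7 to 3.5 points.

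**Step 5: what does one lost success do near the planned effect?** The planned rates on 20 per arm are 16.6 and 7.6, or about 17 against 8. The Pearson statistic is 40·(17·12 − 8·3)² / (20·20·25·15) = 8.64, p = 0.003. With 16 against 8 it is 40·(16·12 − 8·4)² / (20·20·24·16) = 6.67, p = 0.010. The conclusion is the same.

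**The case against.** The other side has a good deal to say.

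- *The criteria are necessary, not sufficient.* An investigator may decline an allergic patient, and 6.4.1 says subjects are pre-selected on medical history. This is true, but it leaves the decision to individual judgement and puts no rule in the protocol.
- *Item 4 may be loosely worded.* If its bracket was meant as examples, a documented contact dermatitis might count as a cutaneous disease. This is possible, but the text does not say so.
- *The product is EC-marked and already marketed.* Its leaflet, the risk analysis report and the consent pages are not in the reviewed text, so a warning there cannot be ruled out. This limits the claim to the protocol and SAP.
- *A reaction caused by the assigned gel is arguably part of the effect of gel plus standard care under ITT.* This is a fair reading, and one reason the measurement issue is secondary.
- *An exclusion for known allergy does nothing about first-time or irritant reactions.* This stands.

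Three stronger conclusions are tempting. The documents support none of them.

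- A reader might infer that a contact reaction would necessarily be graded as radiation dermatitis. Assessors are trained, a third reader settles disagreement, Protocol 14.3 allows signs with another cause to be recorded as adverse events, and SAP 12.3 expects application-site events. But no stated rule removes an adverse event from the grade, so it could happen.
- A reader might infer that a single such failure decides a site's result. A borderline table can be found where it crosses 0.05 (15/20 v 8/20, p = 0.025; 14/20 v 8/20, p = 0.057), but that table is chosen for the purpose. Near the planned effect, one failure changes nothing.
- A reader might infer a risk of a false positive. Any misgrading lowers Group A's success rate, so it works against the gel.

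**Conclusion.** The point holds as an eligibility gap. Neither the protocol nor the SAP excludes a patient with known hypersensitivity to a Table 4 ingredient, and the statement in section 4 that no added risk can be foreseen does not fit with that omission. This part rests on the text alone and needs no prevalence figure.

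The effect on the primary endpoint is a possibility of unknown size, directed against the gel. The 18%, 33% and 64% per site rest on assumed prevalences of 1%, 2% and 5% and describe only the presence of an allergic patient. The power figures rest on assumed values of q. No planned sample size changes.

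**What to change.** Add one exclusion to Protocol 6.3.2 and the synopsis: known hypersensitivity to any ingredient listed in Table 4. Ask about it at visit 1 in all patients, before randomisation, so that both arms are screened alike. Amend the closing sentence of section 4 to acknowledge possible reactions to the gel. The SAP list in section 10 only needs to mirror the protocol; SAP sections 2 and 7 already describe the 80 patients as enrolled, so an SAP edit alone would protect nobody, and a protocol amendment protects only patients randomised after it.

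The cost is one line and one screening question, with no extra visit and very few patients lost at screening. The change does not settle how a first-time reaction is graded. If the team wants that covered too, Protocol 6.4.2 and SAP 9.1 would need a stated rule for attributing and recording suspected contact reactions; this is a separate, optional addition.

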6.4 Procedures

6.4.1 Study visits and assessments

Visit 1 screening (days from -3 to 0):

Subjects will be pre-selected on the basis of their medical history and the need of radiotherapy as curative or postoperative treatment for head & neck or breast cancer. Subjects will be evaluated with regard to the inclusion and exclusion criteria that will allow their participation into the study.

Before any study specific evaluation is carried out, subjects will receive all the information about the study by the Investigators and will sign an informed consent form.

The following assessments will be performed:

- Collection of information about demography
- Medical and surgical history
- Physical examination
- Concomitant medications and therapies
- ECOG performance status
- Erythema assessment
- Skindex-16 questionnaire
- Inclusion/exclusion criteria assessment

Visit 2 – randomization (Day1):

At visit 2 the subject eligibility will be re-assessed. Eligible patients will be randomized 1:1 in the two groups, treated respectively with Xonrid® + SOC or SOC alone.

The radiotherapy will start at this visit.

The following activities will be done at visit 2, before the first RT session:

- Inclusion/exclusion criteria assessment
- Randomization
- Physical examination
- Concomitant medications and therapies
- Erythema assessment
- Skindex-16 questionnaire
- Spettrophotometry examination and TEWL examination
- Treatment dispensation and instructions (the first application will be after RT session)
- Patient's diary dispensation and instructions on how to fill it in every day
- Adverse events recording

Visit 3 to 8/9 – RT and treatment:

Subjects will receive radiotherapy treatment every day for 6 or 7 consecutive weeks, with suspension only in the weekends. Breast cancer subjects are expected to attend 30 radiotherapy sessions (that means 6 weeks) while head & neck cancer subjects are expected to attend 33-35 radiotherapy sessions (that means about 7 weeks). One weekly visit for the study will be performed according to the subject availability (a ± 2 days window will be allowed and any delay will be recovered in the following visits).

The following activities will be done at visits:

- Physical examination
- Concomitant medications and therapies
- Erythema assessment
- Skindex-16 questionnaire
- Spettrophotometry examination and TEWL examination. Both exams will be done with clean skin, before the RT session
- Treatment collection from subject and accountability (only at visit 8/9)
- Diary collection from subject (only at visit 8/9; the diary will be checked for completeness at every visit)
- Treatment dispensation and instructions (only at visit 8/9)
- Diary dispensation to subject (only at visit 8/9)
- Patient Global Satisfaction score (only at visit 8/9)

- Adverse events recording

Visit 9/10 – end of study & end of treatment (Day 56/63):

After RT completion (expected at visit 8/9), all the subjects will go on with their assigned treatment for further 2 weeks.

At day 56 ± 2 or 63 ± 2 days (visit 9/10), depending on cancer typology, a conclusive visit will be performed.

The following activities will be done at conclusive visit:

- Physical examination
- Concomitant medications and therapies
- Erythema assessment
- Skindex-16 questionnaire
- Spettrophotometry examination and TEWL examination. Both exams will be done with clean skin
- Treatment collection and accountability
- Diary collection
- Patient Global Satisfaction score
- Adverse events recording.

